6.5. Study Drug Compliance

For participants in the safety population, overall compliance (%) for INCB050465 will be calculated for all participants as

$$\text{compliance (\%)} = 100 \times [\text{total dose actually taken}] / [\text{total prescribed dose}].$$

The total prescribed dose is defined as the sum of the doses prescribed by the investigator accounting for dose modifications.

The total actual dose taken will be calculated based on information entered on the Drug Accountability eCRF. If there are dispensed drugs that have not been returned yet, the actual dose taken starting from the dispense date of the unreturned drugs will be imputed by the dose taken as reported on the Dosing eCRF.

6.6. Prior and Concomitant Medication

Prior medications and concomitant medications will be coded using the WHO Drug Dictionary. Number and percentage of participants in the FAS population with each prior and concomitant medication will be summarized by WHO drug class and WHO drug PT.

7. EFFICACY

[Appendix A](#) provides a list of planned tables, figures, and listings. Sample data displays are included in a separate document.

7.1. Efficacy Hypotheses

Not applicable.

7.2. Response Assessment

An objective assessment of disease status is required at baseline (screening) using the CT-based response criteria of the Lugano Classification ([Cheson et al 2014](#)). Disease status will be subsequently assessed by CT or MRI every 8 weeks through Week 24, then every 12 weeks through Week 96, and then every 24 weeks thereafter until disease progression.

Bone marrow examination is required as a baseline assessment at screening except for reasons provided in Section 7.6.2 of the Protocol. If disease is present in bone marrow at baseline, a bone marrow examination will be required to confirm CR or may be performed as clinically indicated. If the bone marrow does not have lymphoma involvement at baseline, a repeat marrow examination is not required to confirm indication of CR on imaging.

Sites will use the CT-based response criteria of the Lugano Classification ([Cheson et al 2014](#)) to assess response to treatment locally. At each postbaseline disease assessment, response will be collected in the eCRF as CR, PR, SD, PD, or NE.

All imaging will be submitted to the IRC. Imaging data and applicable clinical data will be reviewed and response assessed using the CT-based response criteria of the Lugano Classification ([Cheson et al 2014](#)) by independent reviewers as described in the Independent Review Charter. An overall timepoint response at each postbaseline disease assessment, the best overall response, the date of initial response (if applicable), and the date of disease progression along with reason(s) of disease progression (if applicable) for each participant, considering radiographic data and clinical data, will be provided by the Clinical Reviewer. These data will be used in the analyses of related efficacy endpoints.

7.3. Analysis of the Primary Efficacy Parameter

The primary efficacy analyses will be conducted when all participants in the FAS who have achieved a response (ie, CR or PR) as determined by IRC have been followed approximately 12 months from the onset of first response.

7.3.1. Best Overall Response and Objective Response Rate

For responses determined by the IRC, the best overall response for each participant will be provided by the Clinical Reviewer. A participant is considered an objective responder if they have a best overall response of CR or PR.

The ORR is the proportion of objective responders. Participants who do not have sufficient baseline or on-study response assessment information to be adequately assessed for response status will be included in the denominators in the calculation of ORR.

Best overall response as determined by the IRC will be summarized descriptively, and the ORR as determined by the IRC with 95% CIs will be calculated. Confidence intervals will be calculated based on the exact method for binomial distributions.

Because participants who switched to the selected treatment regimen after starting the maintenance dose received a mixture of the non-selected and selected maintenance regimens and could confound the efficacy evaluation of the non-selected treatment regimen, a sensitivity analysis of ORR as determined by IRC will be provided to summarize these crossover participants as a separate treatment regimen. In addition, the number of participants who achieved best overall response as determined by IRC after the time of crossover along with the best overall response data will be presented under this separate treatment regimen.

When applicable, sensitivity analysis of ORR as determined by the IRC may be provided excluding participants that do not have evaluable radiological images at baseline per the IRC.

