5.5.1. Criteria for Study Treatment Discontinuation

Subjects **must** be withdrawn from study treatment for any 1 of following reasons:

- The subject has experienced an unacceptable toxicity defined as follows:
 - Occurrence of an AE that is related to study treatment that, in the judgment of the investigator or the sponsor's medical monitor, compromises the subject's ability to continue study-specific procedures or is considered to not be in the subject's best interest.
 - Persistent AE requiring a delay of therapy for more than 2 weeks (14 days) unless a greater delay has been approved by the sponsor.
- The subject is unable to tolerate study treatment.
- The subject has an objective radiographic tumor response of PD.
- Further participation would be injurious to the subject's health or well-being, in the investigator's medical judgment.
- The subject becomes pregnant.
- Informed consent is withdrawn.
Note: Consent withdrawn means that the subject can no longer be followed. Subjects may choose to discontinue study treatment and remain in the study to be followed for disease progression and survival per the schedule of assessments.
- The study is terminated by the sponsor.
- The study is terminated by the local health authority, IRB, or IEC.

A subject **may** be discontinued from study treatment in the following situation:

- If a subject is noncompliant with study procedures or study treatment administration in the investigator's opinion, then the sponsor should be consulted for instruction on handling the subject.

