9.4.1.3. Other Efficacy Analyses

Analyses of ORR, DOR, CRR, and PFS as reported by the investigator will be summarized as described above.

Analyses of ORR, DOR, CRR, PFS as determined by IRC and OS will also be summarized by treatment regimens (A or B) within each cohort.

Health-related quality of life scales as well as change and percentage change from baseline will be summarized descriptively by visit.

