To better understand the safety and efficacy of INCB050465, a total of 70 additional participants (30 participants in Cohort 1 and 40 participants in Cohort 2) will be enrolled into 1 of the 2 treatment regimens being evaluated in this study. The treatment regimen will be selected after enrollment is completed for either Cohort 1 or Cohort 2 (ie, 60 participants enrolled) and after evaluation of emerging safety and efficacy data from this and other monotherapy studies of INCB050465 in non-Hodgkin lymphoma. Once a treatment regimen is selected, the nonselected treatment regimen will be closed to further enrollment. Participants receiving the nonselected treatment regimen may switch to the selected treatment regimen or remain on their current treatment regimen, provided they have not met study-treatment withdrawal criteria and there are no safety concerns for their current treatment regimen. There will be no rebaselining for participants who switch treatment regimens and all participants will continue to follow the same assessment schedule.

Participants will receive treatment until disease progression, death, unacceptable toxicity, or consent withdrawal, whichever occurs first. Participants will be evaluated for ORR by an IRC and followed for DOR, PFS, and OS.

Figure 1: Study Design of INCB 50465-205

EOT = end of treatment; MCL = mantle cell lymphoma; QD = once daily

^a A futility analysis will be performed for each of the cohorts when the first 30 patients in each cohort have been treated and evaluated for response (see Section 9.6). Final analysis will occur when all subjects in the respective Cohort have received at least 1 postbaseline disease assessment, or have progressed, withdrawn from the study, or died.

^b Cohort 1 will be closed to further enrollment by Protocol Amendment 7 with approximately 50 subjects enrolled.

^c Subjects who discontinue study treatment for a reason other than disease progression will continue with disease assessments by radiologic imaging per the Schedule of Assessments.

^d Every 12 weeks by clinic visit, telephone, or e-mail.

^e Urine pregnancy and dispensing of study treatment will occur every 4 weeks.

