7.4. Analysis of the Secondary Efficacy Parameters

7.4.1. Duration of Response

Duration of response is defined as the time from first documented evidence of CR or PR until disease progression or death due to any cause among participants who achieve an objective response (ie, CR or PR), as determined by revised response criteria for lymphomas ([Cheson et al 2014](#)). For responses assessed by the IRC, the date of initial response and date of disease progression will be provided by the Clinical Reviewer for participants who have achieved best response of CR or PR. Censoring of DOR will follow the same algorithm as the censoring of PFS (see Section 7.4.3).

The total number of responders as determined by the IRC, the number of participants whose disease progressed as determined by the IRC or who died, and the number of participants censored will be summarized. The Kaplan-Meier estimate of median DOR as determined by the IRC and its 95% CIs will be provided, with the CIs calculated using the generalization of Brookmeyer and Crowley's method (1982) with log-log transformation ([Klein and Moeschberger 1997](#)).

A sensitivity analysis of DOR will be performed where response assessments after the time of crossover will be excluded from the determination of DOR for participants who switched to the selected treatment regimen after starting the maintenance dose. Crossover participants who have not progressed at the time of crossover will be censored at the last valid radiologic assessment on/before the time of crossover. Participants who failed to achieve a response of CR or PR on/before the time of crossover will not be considered as responders for this analysis.

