7.4.2. Complete Response Rate

Complete response rate is the percentage of participants with a best overall response of CR as defined by revised response criteria for lymphomas ([Cheson et al 2014](#)). For responses determined by the IRC, the best overall response for each participant will be provided by the Clinical Reviewer. Participants who do not have sufficient baseline or on-study response assessment information to be adequately assessed for response status will be included in the denominators in the calculation of CRR.

The CRR as determined by the IRC will be estimated with 95% CIs. Confidence intervals will be calculated based on the exact method for binomial distributions.

A sensitivity analysis of CRR will be provided to summarize participants who switched to the selected treatment regimen after starting the maintenance dose as a separate treatment regimen.

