2.4.2	Summary of Best Overall Response and Objective/Complete Response Rate as Reported by Investigator – Crossover as a Separate Treatment Group	FAS	
2.4.3	Summary of Best Overall Response as Determined by Independent Review Committee for Crossover Participants	FAS	
2.4.4	Summary of Best Overall Response as Reported by Investigator for Crossover Participants	FAS	
2.4.5	Summary of Duration of Response as Determined by Independent Review Committee – Censoring Crossover Participants	FAS	
2.4.6	Summary of Duration of Response as Reported by Investigator – Censoring Crossover Participants	FAS	
2.4.7	Summary of Progression-Free Survival as Determined by Independent Review Committee – Censoring Crossover Participants	FAS	
2.4.8	Summary of Progression-Free Survival as Reported by Investigator – Censoring Crossover Participants	FAS	
Safety			
3.1.1	Summary of Exposure and Compliance	Safety	
3.1.2	Summary of Exposure and Average Daily Dose During Initial QD Dosing Period	Safety	
3.1.3	Summary of Exposure and Average Daily Dose During Maintenance Dosing Period	Safety	
3.2.1	Overall Summary of Treatment-Emergent Adverse Events	Safety	X
3.2.2	Summary of Treatment-Emergent Adverse Events by MedDRA System Organ Class and Preferred Term	Safety	X
3.2.3	Summary of Treatment-Emergent Adverse Events by MedDRA Preferred Term in Decreasing Order of Frequency	Safety	X
3.2.4	Summary of Treatment-Emergent Adverse Events by MedDRA System Organ Class, Preferred Term, and Maximum Severity	Safety	X
3.2.6	Summary of Grade 3 or Higher Treatment-Emergent Adverse Events by MedDRA System Organ Class and Preferred Term	Safety	X

Table No.	Title	Population	Standard
3.2.7	Summary of Grade 3 or Higher Treatment-Emergent Adverse Events by MedDRA Preferred Term in Decreasing Order of Frequency	Safety	X
3.2.8	Summary of Serious Treatment-Emergent Adverse Events by MedDRA System Organ Class and Preferred Term	Safety	X
3.2.9	Summary of Serious Treatment-Emergent Adverse Events by MedDRA Preferred Term in Decreasing Order of Frequency	Safety	X
3.2.10	Summary of Treatment-Related Treatment-Emergent Adverse Events by MedDRA System Organ Class and Preferred Term	Safety	X
3.2.11	Summary of Treatment-Related Treatment-Emergent Adverse Events by MedDRA Preferred Term in Decreasing Order of Frequency	Safety	X
3.2.12	Summary of Treatment-Related Treatment-Emergent Adverse Events by MedDRA System Organ Class, Preferred Term, and Maximum Severity	Safety	X

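### Maintenance-period safety tables count switchers' time and events on the non-selected regimen under Crossover, and the crossover ORR/CRR tables leave that regimen a selected remainder (supportive tables only)

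*SAP*

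**What the plan says.** **Who can switch.** Once a regimen is selected, participants on the other one may switch, "provided they have not met study-treatment withdrawal criteria" (SAP 3). Protocol 5.5.1 lists those criteria; besides unacceptable toxicity, one is "The subject has an objective radiographic tumor response of PD". The Amendment 1 notes in SAP 11.2 record that B (2.5 mg QD) was selected, so A is the non-selected regimen.

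**Safety.** SAP 5.2 puts participants who switch after the start of maintenance in a separate Crossover regimen for maintenance-period safety summaries, and in their assigned regimen for everything else. SAP 6.4 measures maintenance duration from the first maintenance dose to the last dose. SAP 9.2.3 groups the maintenance TEAE tables in the same way. None of these sections divides a switcher's time or events at the switch.

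**Response.** For ORR, "a sensitivity analysis of ORR as determined by IRC will be provided to summarize these crossover participants as a separate treatment regimen" (7.3.1). For CRR, "A sensitivity analysis of CRR will be provided to summarize participants who switched to the selected treatment regimen after starting the maintenance dose", again as a regimen of their own (7.4.2). These are Tables 2.4.1 and 2.4.2.

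**What is already planned alongside.** Under Protocol 9.4.1.3, ORR, CRR, DOR, PFS and OS "will also be summarized by treatment regimens (A or B) within each cohort"; by SAP 5.2 these tables keep switchers in the assigned regimen (Table 2.1.1 for response). The DOR sensitivity analysis cuts at crossover: "Participants who failed to achieve a response of CR or PR on/before the time of crossover will not be considered as responders" (7.4.1). Table 2.4.3 is the "Summary of Best Overall Response as Determined by Independent Review Committee for Crossover Participants".

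**The concern.** SAP 11.2 describes the period-specific TEAE tables as support for the safety profile of the maintenance dose. The two maintenance regimens exist to see whether adverse events leading to withdrawal become less frequent (Protocol 1.4 and 1.5), so it matters which regimen a participant was taking when an event began. As written, a Grade 3 event on A before the switch is tabulated under Crossover. No planned summary shows maintenance on A for everyone assigned to A: the maintenance tables omit switchers' time on A, and the overall-period tables add their later time on B.

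In the response tables the grouping depends on what happened after baseline. A participant must still be on treatment, without progression, to switch. The A row keeps all the early progressors and loses some participants with lasting benefit. SAP 7.3.1 adds the table because switchers might confound evaluation of the non-selected regimen, yet the layout brings in a selection effect of its own. A reader could take a low A row for a regimen effect.

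**Working it through.** The documents give no number of switchers and no allocation ratio, so the plan has no figure on this point to reproduce. The 60% response rate is the Cohort 2 planning value (SAP 3.3); 30 participants in A is an assumption.

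**1. Response rows, exact arithmetic.** With n assigned to A, R responders, and k switchers of whom r responded:
- A row = (R − r)/(n − k); Crossover row = r/k.
- There is no shift when r/k = R/n.

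Take n = 30, R = 18 (60%), k = 10:

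| Responders among 10 switchers | A row | Crossover row |
|---|---|---|
| 6 | 12/20 = 60% | 6/10 = 60% |
| 8 | 10/20 = 50% | 8/10 = 80% |
| 9 | 9/20 = 45% (exact 95% CI 23–68%) | 9/10 = 90% |

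With few switchers the shift is small: 3 switchers with 2 responders leave 16/27 = 59.3%. With 25 in A (R = 15) or 35 in A (R = 21), the 9-of-10 case gives 6/15 = 40% or 12/25 = 48%.

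**2. Simulation with identical regimens.** All inputs are assumed:
- 30 in A; entry uniform over 16 months; selection at month 18; cutoff 14 months later.
- Response at Week 8; median DOR 14 months; non-responder median PFS 3 months.
- Hazards of 0.03 per month for AE discontinuation and 0.04 per month for Grade 3 or higher TEAEs in maintenance, the same before and after the switch.
- Eligible to switch = in maintenance and on treatment at selection. On average this is 11.2 of 30, of whom 85% are responders.

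Share of A maintenance time placed under Crossover = switchers' time from first maintenance dose to switch, divided by that time plus the maintenance time of those who stayed on A. Safety percentages use participants who started maintenance as the denominator.

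| Share of eligible who switch | 30% | 60% | 100% | As assigned |
|---|---|---|---|---|
| A maintenance time under Crossover | 12% | 27% | 59% | 0% |
| A, Grade ≥3 TEAE, current layout | 23% | 20% | 13% | 25% |
| A, Grade ≥3 TEAE, after split | 23% | 20% | 16% | 25% |
| A, AE discontinuation, current layout | 25% | 26% | 26% | 25% |
| A, AE discontinuation, after split | 22% | 19% | 14% | 25% |
| A row ORR, Table 2.4.1 | 57% | 53% | 45% | 60% |

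In all three cases the Crossover row shows an ORR of 85% and a Grade ≥3 percentage of about 40%. About 51% of its first Grade ≥3 events predate the switch. Counting any event after the switch, the figure is about 25%; counting only participants whose first event came after it, 20%.

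For CRR, suppose half of responders can reach CR, half of these at first response and the rest after a median of 4 months. The as-assigned CRR is then 26.6%, the A row 24.9%, 22.7% and 18.5%, and Crossover 40%.

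**3. Sensitivity to the inputs.** When the inputs are varied, the share of A time under Crossover ranges from 7% to 67%, and the share of first Grade ≥3 events predating the switch from 38% to 77%. A second simulation used responder medians of 6–18 months, non-responder medians of 2–4 months and 25–90% of eligible participants switching. It gave an A row of 33–59%, a Crossover row of 74–95%, and 5.5–8.7 months of A maintenance per switcher counted under Crossover. If non-responders switch more readily (100% of eligible non-responders, 30% of eligible responders), the effect on response nearly vanishes: A about 60%, Crossover 63%.

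**The case against.** **The plan already covers most of the ORR question.** Table 2.1.1 gives as-assigned ORR by regimen, the DOR sensitivity analysis counts responders up to crossover, and Table 2.4.3 shows best responses reached afterwards. The regimens are the same for the first 8 weeks, and the MCL responses in the earlier study had all appeared by the 9-week scan (Protocol 1.3). A pre-crossover ORR would therefore be 60% if all responses come by Week 8, and 59%, 59% and 58% if a quarter come at Week 16 or 24. This stands, and makes that table optional.

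**A pre-crossover CRR can mislead too.** It gives no credit for later conversion from PR to CR and truncates A but not B. It reads 25.9%, 25.1% and 24.1% against 26.6%. In about 10% of the 486 assumption sets tried it understates A by more than the criticised row does; that is a share of a chosen grid, not a probability. This stands.

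**Splitting does not repair the percentages.** The table above shows Grade ≥3 percentages for A hardly improve, and AE-discontinuation percentages move further from 25%. This stands: the gain lies in correct attribution and in person-time, and exposure-adjusted rates assume a roughly constant risk, which Protocol 5.4.4 does not establish.

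**A table note may already exist.** The shells are in a separate document, SAP 7.3.1 itself says switchers received a mixture, and the table titles name Crossover as a separate group. The absence of a note cannot be confirmed.

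**Stronger readings.** A reader might infer that the primary ORR is biased. It is not: Protocol 9.4 pools A and B for primary and secondary efficacy, so row placement cannot matter. A reader might also infer that a regimen comparison is distorted, but SAP 3.2 and 5.2 plan none.

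**Conclusion.** The point holds and is minor. On the text, maintenance time and events on A before a switch are shown under Crossover, and the A row in Tables 2.4.1–2.4.2 is a remainder selected after baseline. The direction for response is a tendency, with no shift if responders are as common among switchers as in all of A. The sizes rest on assumed switching, accrual, response duration and event rates, and on 30 participants in A; the documents do not allow them to be fixed.

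Only supportive or descriptive tables are affected: maintenance-period exposure and TEAEs, and the crossover ORR/CRR tables. The pooled primary and secondary efficacy analyses, the main by-regimen efficacy tables and the overall-period tables (as as-assigned summaries) are not. Nor do the figures show that A would always look worse or better on safety: its Grade ≥3 percentage reads low under the current layout, while its AE-discontinuation percentage barely moves.

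**What to change.** 1. **SAP 5.2, 6.4 and 9.2.3.** Split maintenance exposure and TEAEs at the crossover date: before the switch under the non-selected regimen, after it under Crossover. Show person-time and exposure-adjusted rates beside the percentages, and state that percentages for A are cut short at the switch and that the rates assume a roughly constant risk. Cost: a wording change in three sections and modest programming on data already collected.

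2. **Tables 2.4.1–2.4.4.** Keep them as descriptive. Add a note that the grouping is post-baseline and that the A row does not estimate the regimen's effect, and refer readers to Table 2.1.1. Under the rule in SAP Appendix A on changes to the table lists, a note should not need an amendment.

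3. **Optional, SAP 7.3.1 and 7.4.2.** Add ORR and CRR by assigned regimen over the full denominator, counting only responses on or before crossover (the 7.4.1 rule), with exact 95% CIs. For CRR the source exists: the IRC supplies "An overall timepoint response at each postbaseline disease assessment" (SAP 7.2). Read the result only as a lower bracket to Table 2.1.1, and state that it truncates A but not B. As new estimates, these need wording in both sections. The downside is that A reads lower: with 30 in A, one later response turns 18/30 = 60% into 17/30 = 57%, and two later CRs turn 6/30 = 20% into 4/30 = 13%.
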